Patients should bring all unused and used study drugs to each study visit. Study drug accountability will be conducted, and results will be recorded. If a patient is persistently noncompliant with the study treatment, it may be appropriate to withdraw the patient from the study (see Section 4.5). All patients should be reinstructed about the dosing requirement during study contacts. The authorized study personnel conducting the re-education must document the process in the patient's source records.

5.9. **Prior and Concomitant Medications and Non-Drug Therapies**

5.9.1. **Prohibited Medications**

Table 5-2 provides examples of prohibited drug categories; however, it is not a comprehensive list of all restricted medications. Drugs and drug classes in Table 5-2 are prohibited at any time during the study through the to the Safety Follow-up visit, except as noted in the table. Consult the medical monitor if there is any uncertainty regarding patient use of a particular drug or drug class.

Table 5-2 Prohibited Medications

Drug Class	Examples	Comments
Bisphosphonates	alendronate	
	etidronate	
	zoledronic acid	
GnRH Analogues	leuprolide acetate injection, also	
_	known as leuprorelin	
	goserelin acetate injection	
Anti-Androgens	danazol	
Anti-convulsant drugs	phenobarbital	All other anticonvulsants are
(specified)	carbamazepine	allowed.
	phenytoin	
	valproic acid	
	primidone	
Aromatase Inhibitors	anastrozole	
	letrozole	

Drug Class	Examples	Comments
Progestins and progestin	dienogest	
implants	norethindrone	
•	medroxyprogesterone	
	cyproterone	
	etonogestrel	
Estrogens	estradiol valerate	
8	conjugated estrogens	
	ethynyl estradiol	
Hormonal	combined or progestin only	
Contraceptives,	NuvaRing	
contraceptive patches and	1 (a varting	
vaginal rings		
Selective Estrogen	raloxifene	
Receptor Modulators	bazedoxifene	
Receptor Wodulators	lasofoxifene	
	clomifene	
	tamoxifen	
C-1		
Selective Progesterone	mifepristone	
Receptor Modulators	ulipristal acetate	
Over-the-counter and	plant-based estrogen products	
herbal products/teas with	"natural" thyroid supplements	
known hormonal activity	dihyroepiandrosterone (DHEA)	
Intrauterine Devices	Levonorgestrel intrauterine system	
Bone Agents	calcitonin	Calcium and Vitamin D2 and
	calcitriol	Vitamin D3 (ergocalciferol and
	ipriflavone	cholecalciferol) are allowed without
	teriparatide	restriction.
	denosumab	
	abaloparatide	
	odanacatib	
	romosozumab	
Anti-Coagulants/	warfarin	
Platelets/Fibrinolytics	clopedigril	

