	tranexamic acid	
	vitamin k preparations	
	factor Xa inhibitors	
Glucocorticoids	prednisolone or prednisone	Anticipated use (at screening) of
	dexamethasone	systemic glucocorticoids at an oral
		prednisone-equivalent dose of more
		than 5 mg every other day during
		the study is prohibited. Note:
		topical, inhaled, intranasal, otic,
		ophthalmic, intraarticular, or
		intralesional subcutaneous are
		permitted without restriction.
		Short duration (≤ 21 days) higher-
		dose glucocorticoids required for
		acute events are permitted during
		the study.
		me study.

Drug Class	Examples	Comments
P-glycoprotein Inducers	avasimibe carbamazepine phenytoin rifampin St. John's Wort tipranavir/ritonavir	For patients requiring a short course of these drugs during the study, investigator must contact the medical monitor for approval and guidance on study drug administration during this period.
Moderate and Strong P-glycoprotein Inhibitors	amiodarone azithromycin ^a captopril ^b carvedilol ^g clarithromycin ^a conivaptan cyclosporin ^c diltiazem dronedarone erythromycin ^a felodipine ^d itraconazole ^e ketoconazole ^e lopinavir/ritonavir ^f quercetin quinidine ranolazine ticagrelor verapamil	For patients requiring a short course of these drugs during the study, investigator must contact the medical monitor for approval and guidance on study drug administration during this period.

Abbreviation: GnRH, gonadotropin-releasing hormone

- a. Roxithromycin is allowed
- b. All other angiotensin converting enzyme inhibitors are allowed
- c. Tacrolimus is allowed
- d. Amlodipine and nifedipine are allowed
- e. Fluconazole is allowed
- f. Integrase inhibitors are allowed
- g. Metoprolol and atenolol are permitted

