5.9.3. Prohibited Non-Drug Therapies

Surgical and other interventional treatment of uterine fibroids is prohibited from the Week 52/Baseline visit until the patient's final study visit unless urgently needed for patient safety.

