2.2. Sample Size Considerations

Because this is an extension of study MVT-601-3003, the sample size of this study was based on approximately the number of patients who completed a pivotal study (n = 780 patients in total), and who participated in the LTE study (n = 600 patients in total assuming about 20% dropout rate at 6 months from the pivotal studies). Assuming the proportion of responders at Week 52 in MVT-601-3003 LTE study is 60%, it was estimated that approximately 360 patients were to be randomized into this study.

With 360 patients, the study would have at least 90% power to detect a difference of 20% or greater between relugolix+ E2/NETA group and placebo group for the primary endpoint. The following assumptions were used to determine the sample size for this study:

- 2-sided type I error rate: 0.05
- Randomization: 1:1
- Responder rate for placebo group: 40%
- Responder rate for relugolix + E2/NETA group: 60%
- Dropout rate: 20%

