Assessments will be excluded from analysis if they occur on or after the date of initiation of another investigational agent or hormonal therapy affecting the hypothalamic-pituitary-gonadal axis or surgical intervention for uterine fibroids. Assessments after date of last dose of study drug + 60 days will also be excluded from analysis.

Table 4: Visit Windows for UFS-QoL Assessments

Visit (Long label)	Visit (Short label)	Start Day	Target Day	End Day
Week 64 (12 weeks after randomization)	Week 64	64	85	106
Week 76 (24 weeks after randomization)	Week 76	148	169	196
Week 88 (36 weeks after randomization)	Week 88	197	253	308
Week 100 (48 weeks after randomization)	Week 100	309	337	351
Week 104 (52 weeks after randomization)	Week 104	352	365	421

Abbreviations: UFS-QoL = Uterine Fibroid Symptom and Health-Related Quality of Life.

Table 5: Visit Windows for Clinical Laboratory Tests and Vital Signs

Visit (Long label)	Visit (Short label)	Start Day	Target Day	End Day
Week 64 (12 weeks after randomization) ^a	Week 64	64	85	106
Week 76 (24 weeks after randomization)	Week 76	148	169	196
Week 104 (52 weeks after randomization)	Week 104	309	365	Date of last dose + 6 days
Safety Follow-Up ^b	Safety Follow-Up	Date of last dose + 7 days	Date of last dose + 30 days	Date of last dose + 60 days

^a This visit is only for clinical laboratory tests.

^b The safety follow-up visit window will be restricted to assessments prior to the date of initiation of another investigational agent or hormonal therapy affecting the hypothalamic-pituitary-gonadal axis or surgical intervention for uterine fibroids.

Table 6: Time Window for Feminine Product Collection

Visit (Long label)	Visit (Short label)	Feminine Product Collection Visit Date ^{a,b}	Time Window ^a
Week 56 (4 weeks after randomization) ^a	Week 56	X ₁	(Date of Study Day 1) – < X ₁
Week 60 (8 weeks after randomization)	Week 60	X ₂	(X ₁ +1) – ≤ X ₂
Week 64 (12 weeks after randomization)	Week 64	X ₃	(X ₂ +1) – ≤ X ₃
Week 68 (16 weeks after randomization)	Week 68	X ₄	(X ₃ +1) – ≤ X ₄
Week 72 (20 weeks after randomization)	Week 72	X ₅	(X ₄ +1) – ≤ X ₅
Week 76 (24 weeks after randomization)	Week 76	X ₆	(X ₅ +1) – ≤ X ₆
Week 80 (28 weeks after randomization)	Week 80	X ₇	(X ₆ +1) – ≤ X ₇
Week 84 (32 weeks after randomization)	Week 84	X ₈	(X ₇ +1) – ≤ X ₈
Week 88 (36 weeks after randomization)	Week 88	X ₉	(X ₈ +1) – ≤ X ₉
Week 92 (40 weeks after randomization)	Week 92	X ₁₀	(X ₉ +1) – ≤ X ₁₀

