5.2. Protocol Deviations

Protocol deviations that occurred during the randomized withdrawal study will be categorized as important or minor per the protocol deviation plan. Important protocol deviations will include, but will not be limited to, the following categories:

- Randomized patient who did not satisfy key entry criteria;
- Randomized patient who met withdrawal criteria during the study but was not withdrawn;
- Randomized patient who received the wrong treatment;
- Randomized patient who received a prohibited concomitant medication that met criteria for an important protocol deviation;
- Unintentional unblinding of treatment assignment.

Important protocol deviations will be summarized by deviation category for all patients in the mITT population. A patient listing of all important protocol deviations will be provided.

A selected subset of the major protocol deviations that are likely to affect analysis of efficacy will be identified to define the Per-Protocol population prior to the database lock. This subset will include but will not be limited to the following important protocol deviations:

- Did not satisfy key entry criteria (restricted to patients who did not meet inclusion criterion 4 of MVT-601-035, ie, patients who were not responders at the time eligibility was being assessed);
- Drug compliance during the randomized treatment period < 75%;
- Patient received prohibited concomitant medications that met criteria for important protocol deviation: restricted to patients who received prohibited concomitant medications that may cause significant drug-drug interaction;

- Unintentional unblinding of treatment assignment.

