7.3.1.2. Censoring Rules

The censoring rules in the Kaplan-Meier method are described as the following (see Table 8):

- For patients with relapse (MBL volume ≥ 80 mL) during the randomized treatment period, they will be considered as having an event at the time of first relapse. The time of first relapse is the date of the earliest menstrual bleeding days within the first FP collection visit window in which the MBL volume is ≥ 80 mL.
- For patients who did not have relapse during the randomized treatment period and had complete FP collection at each scheduled visit during the randomized treatment period,

they will be considered as not having an event and will be censored at the last available FP collection visit date during the randomized treatment period.

- For patients who did not have relapse during the randomized treatment period and had incomplete or missing FP collection during the randomized treatment period, they will be considered as censored using the following censoring rules:
 - If patients did not have FP collection after Week 64 (ie, have up to 3 FP collection visits through Week 64), they will be censored at the date of the last available FP collection visit if there are no consecutive visits with incomplete or missing FP collection; they will be censored at the date of the last available FP collection visit prior to the consecutive visits with incomplete or missing FP collections if there are two or more consecutive visits with incomplete or missing FP collections.
 - If patients had FP collection after Week 64
 - did not have incomplete or missing FP collections at consecutive visits, they will be censored at the last available FP collection date during the randomized treatment period.
 - had two or more consecutive visits with incomplete or missing FP collections, they will be censored at the last available FP collection visit date prior to the two consecutive visits during the randomized treatment period.

The time to event or censoring will be summarized by the Kaplan-Meier method. If the event time or censoring time is after the target (Day 365), Day 365 will be used as the event time or censoring time.

A sensitivity analysis will be performed considering different censoring rules (see Section [7.3.4.3](#)).

Table 8: Censoring Rules for Kaplan-Meier Analysis During Randomized Treatment Period

Type of Patients	Event	Event Time ^a	Censored	Censoring Time ^a

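### The Per-Protocol medication exclusion covers only interacting drugs, and no planned analysis of the Week 76 rate accounts for bleeding-suppressing prohibited treatment started before relapse

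*SAP*

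**What the plan says.** SAP 5.2 first treats receipt of a prohibited medication as one kind of important deviation. It then selects the subset that defines the Per-Protocol population, described as deviations likely to affect the efficacy analysis. In that subset the medication item is "restricted to patients who received prohibited concomitant medications that may cause significant drug-drug interaction". The other listed items are failure of the responder entry criterion, compliance below 75% and unintentional unblinding. The list is stated to be non-exhaustive and is settled before database lock.

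Protocol Table 5-2 prohibits more than interacting drugs. It also bars GnRH analogues, danazol, progestins, estrogens, hormonal contraceptives, selective progesterone receptor modulators (SPRMs), the "Levonorgestrel intrauterine system" and "tranexamic acid". Protocol 5.9.3 adds procedures: "Surgical and other interventional treatment of uterine fibroids is prohibited from the Week 52/Baseline visit", with an exception for urgent patient safety.

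For the primary endpoint, SAP 7.3.1.2 and Table 8 assign events and censoring. For a woman with no relapse and complete collections, "they will be considered as not having an event and will be censored at the last available FP collection visit date". Table 9 derives responder status from measured loss, product return rate and the reason for non-collection. Reported amenorrhea is set to 0 mL and counts as response.

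**The concern.** The subset is meant to remove women whose deviation could distort the efficacy result. A drug or procedure that itself reduces menstrual blood loss acts on the measured quantity, yet it is the kind of deviation that the medication item leaves out. The filter fits the placebo arm least well. An interaction with relugolix cannot matter to a woman who is not taking it, so a placebo patient on a P-glycoprotein inhibitor could be removed while a placebo patient on a progestin stays.

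The mITT analysis has a separate gap. If bleeding is held below 80 mL by something other than randomized drug, the woman adds event-free time, possibly through Day 169, and the estimate credits her arm with maintained response. What is at stake is whether the Week 76 difference can be read as the effect of continuing against withdrawing relugolix with E2/NETA, and whether any planned analysis would show if it cannot.

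**Working it through.** **Step 1: the rules side by side.** Each place in the SAP where such a woman could be caught:

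| Rule | What it uses | Bleeding-suppressing treatment before relapse? |
|---|---|---|
| 7.3.1.2, Table 8 (events, censoring) | first loss ≥ 80 mL; complete, incomplete or missing collection | not mentioned |
| 7.3.3, Table 9 (responder status) | loss, return rate, reason for no collection | not mentioned; amenorrhea of any cause is response |
| Sensitivity Analysis 1 | Week 76 completers | not mentioned |
| Sensitivity Analysis 2 | Per-Protocol set | only if the drug also interacts, or if added later |
| Sensitivity Analysis 3 | missing collections recoded as events | not mentioned |

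Sensitivity Analysis 2 may also not be run: SAP 4.2.2 drops it if the Per-Protocol set exceeds 95% of the mITT population. Protocol 4.5 does not name prohibited medication or fibroid surgery as a reason for removal from therapy, although its gross non-compliance item could be used at discretion. A woman can therefore remain on randomized drug after starting such a treatment.

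**Step 2: who is affected.** Only women treated before their first loss ≥ 80 mL and while on randomized drug. A relapse that came earlier is already an event. A woman who stops randomized drug is censored, so she is not carried as a responder to Week 76.

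**Step 3: the plan's power figure.** Inputs from SAP 2.2: "2-sided type I error rate: 0.05"; "Randomization: 1:1"; 60% against 40%; 360 patients; 20% dropout. Evaluable per arm: 360 × 0.80 / 2 = 144. The two-proportion formula with pooled variance under the null is

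z = [d√n − 1.96√(2p̄(1−p̄))] / √(p₁(1−p₁) + p₂(1−p₂)).

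With d = 0.20 and p̄ = 0.50: (2.400 − 1.386) / 0.693 = 1.464, so power is 0.928. This agrees with the stated minimum of 90%. It approximates the SAP's fixed-time Kaplan-Meier test.

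**Step 4: illustration.** Assume that a share c of would-be relapsers in an arm is masked. The placebo rate becomes 0.40 + 0.60c and the relugolix rate 0.60 + 0.40c. The documents give no value for c; 2% to 15% is an assumed range.

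| Masked share c | Placebo rate | Relugolix rate | Difference (points) | Power at 144 per arm |
|---|---|---|---|---|
| none | 0.400 | 0.600 | 20.0 | 0.928 |
| placebo 2% | 0.412 | 0.600 | 18.8 | 0.895 |
| placebo 5% | 0.430 | 0.600 | 17.0 | 0.826 |
| placebo 10% | 0.460 | 0.600 | 14.0 | 0.664 |
| placebo 15% | 0.490 | 0.600 | 11.0 | 0.466 |
| relugolix 5% | 0.400 | 0.620 | 22.0 | 0.966 |
| relugolix 10% | 0.400 | 0.640 | 24.0 | 0.985 |
| relugolix 15% | 0.400 | 0.660 | 26.0 | 0.995 |
| both 5% | 0.430 | 0.620 | 19.0 | 0.902 |
| both 10% | 0.460 | 0.640 | 18.0 | 0.870 |

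In head counts, would-be placebo relapsers number 0.60 × 144 = 86.4, so 5% is about 4 women and 10% about 9. The higher power in the relugolix rows is not a gain: it comes from an inflated difference.

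**The case against.** The strongest reply is that the plan leaves room to handle these women. The Per-Protocol list is open-ended, its governing criterion is likely effect on efficacy, and it is fixed before unblinding. A progestin or a fibroid procedure fits that criterion. This stands: a reader might infer that the Per-Protocol analysis is bound to keep such women, and the documents do not say so. They say only that the medication item is restricted and that any addition would be a later judgement.

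A reader might also infer that the Per-Protocol rule is what makes these women responders. It is not. That set feeds only Sensitivity Analysis 2; the mITT result follows from Tables 8 and 9.

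The group is probably small. Women anticipating prohibited drugs or expecting fibroid surgery are ineligible, products are returned every 4 weeks, and a first loss ≥ 80 mL brings an offer of open-label treatment. Protocol 2.1 describes tranexamic acid and danazol as having limited clinical effectiveness, so use need not mask relapse. All of this stands.

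It is tempting to point to the bone density rule in SAP 4.3.7, "Assessments will be excluded from analysis if they occur on or after the date of initiation of another investigational agent or hormonal therapy", as proof that the sponsor saw the problem for safety and overlooked it for efficacy. The contrast is weak. That window runs to Day 449 and admits scans up to 60 days after the last dose, when other therapy is expected. Blood-loss collection ends 7 days after the last dose.

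It is also tempting to call the bias conservative, because bleeding returns more often off drug. That holds only if masking is mainly on placebo, and the documents do not establish the direction.

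Finally, ignoring concomitant treatment is a legitimate treatment-policy choice for a primary analysis, and deviations and concomitant medications will be tabulated by group. But neither document states that choice for blood loss, and a tabulation does not show the effect on the Week 76 rate.

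**Conclusion.** The point holds as a gap in pre-specification. The medication item in SAP 5.2 is narrower than the purpose stated for the subset, and fibroid procedures are not listed. The primary rules and the three sensitivity analyses make no provision for bleeding-suppressing prohibited treatment started before relapse on randomized drug. In the mITT analysis such a woman is event-free.

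The size is unknown. Over the assumed range of 2% to 15% masked in one arm, the 20-point planning difference lies between 11 and 26 points, with the sign of the shift set by the arm. These figures rest on the planning rates, 144 evaluable per arm and complete masking in the affected women. They show sensitivity, not expected bias. They do not support reading the trial as underpowered, or its result as biased in a known direction. The change should be made because it is cheap and makes the supportive analyses test what they are meant to test.

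**What to change.** 1. In SAP 5.2, widen the Per-Protocol medication item to prohibited medications that may cause a significant drug-drug interaction or that directly affect menstrual blood loss. Examples are GnRH analogues, danazol, progestins, estrogens, hormonal contraceptives, the levonorgestrel system, SPRMs and tranexamic acid. Anticoagulants belong here too, for Per-Protocol exclusion only. Add an item for any fibroid procedure during the randomized period before relapse.

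2. In SAP 7.3.4, add one mITT sensitivity analysis of the Week 76 sustained responder rate. Starting a bleeding-suppressing prohibited treatment, or having a fibroid procedure, before relapse counts as an event on its start date. Limit it to bleeding-suppressing treatments. Leave out anticoagulants and SERMs, because counting their start as relapse would create false events. If such treatment is mainly on placebo, this run will favour relugolix, so it should sit beside the primary analysis and not replace it.

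The cost is SAP wording and one more run of the same Kaplan-Meier code. Medication start and stop dates are already recorded (Protocol 5.9.2), and the bone density rule already relies on dates of hormonal therapy and fibroid surgery. The Per-Protocol set becomes slightly smaller. No clinical rule changes.

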5.3. Demographic and Baseline Characteristics

Demographic and Baseline characteristics at pivotal study baseline (Pivotal Baseline) and at this randomized withdrawal study baseline (Week 52/Baseline) will be summarized by treatment group for the mITT population. Categorical data will be summarized using frequencies and percentages, by treatment group and overall (see Table 7 below) for each baseline. Summaries of continuous data will display the mean, SD, median, minimum, and maximum. The numbers of missing values will also be summarized.

Table 7: Categories for Demographic and Baseline Characteristics

Variable	Category
For both Pivotal Baseline and Week 52/Baseline	
Age (years)	< 40, ≥ 40
BMI (kg/m ²)	< 18.5, 18.5 to <25, 25 to <30, 30 to < 35, 35 to < 40, ≥ 40
	< 30, ≥ 30
UFS-QoL Bleeding and Pelvic Discomfort Scale	0 to < 25, 25 to <50, 50 to <75, 75 to 100
Patient Global Assessment	
Function	No limitation at all, Mild limitation, Moderate limitation, Quite a bit of limitation, Extreme limitation
Symptoms	Not severe, Mildly severe, Moderately severe, Very severe, Extremely severe
Hemoglobin (g/dL)	Min to < 8, ≥ 8 to <10.5, ≥ 10.5 to <12, ≥ 12
For Week 52/Baseline Only	
Geographic region	North America, Other
	North America, Europe, Latin America, Rest of World
Duration of relugolix exposure prior to randomization (weeks)	28, 52
For Pivotal Baseline Only	
Race	Black or African American, White, American Indian or Alaska Native, Asian, Native Hawaiian or Other Pacific Islander, Other
Ethnicity	Hispanic or Latino, Not Hispanic or Latino, or Not reported
Menstrual blood loss volume at baseline (mL)	< 225, ≥ 225
Menstrual blood loss volume at baseline (mL)	< 160, ≥ 160

Variable	Category
History of prior pregnancy	Yes, No
Disease duration of uterine fibroid (years)	Min to <1, ≥ 1 to < 3, ≥ 3 to <5, ≥ 5 to <10, ≥ 10
Type of uterine fibroids	
Subserous fibroid	Yes, No
Intramural fibroid	Yes, No
Submucosal fibroid	Yes, No
Other	Yes, No
Any surgery for uterine fibroids	Yes, No
Volume of myoma at Pivotal Baseline (cm ³)	< 25, ≥ 25
Volume of uterus at Pivotal Baseline (cm ³)	< 300, ≥ 300
Maximum NRS score for uterine fibroid-associated pain at Pivotal Baseline	< 4, ≥ 4
Alcohol use	None, Moderate (2 - 6 drinks per week), Heavy (≥ 7 drinks per week)
Smoking history	Current smoker, Past smoker, Never

Abbreviations: BMI = body mass index; NRS = Numerical Rating Scale; UFS-QoL = Uterine Fibroid Symptom and Health-Related Quality of Life.

